1. INTRODUCTION

In recent years the cosmetic industry has grown considerably, along with its concern for developing safe and effective products. This industry awareness, and consumer and regulatory agency requirements have led cosmetic manufacturers to adopt procedures that provide them with a better understanding of their products. This includes the conduct of clinical tests to assess safety and efficacy, which are often coordinated by dermatologists or other experts before marketing a product. These procedures provide greater assurance of safety for the companies, increase their credibility, and increase confidence among consumers.

A cosmetic product that is freely available to the consumer must be safe when applied under normal or reasonably foreseeable conditions of use (ANVISA, 2012). Thus, the raw materials used in the product formulation must be of proven safety and with established use in the cosmetic industry. As a general requirement, the safety of the final formulation must also be confirmed before it is marketed.

Skin contact with topical products such as cosmetics may trigger different types of reactions including eczematous contact dermatitis, urticaria, acne and spots. Contact dermatitis can arise from two mechanisms: primary irritation, through the action of irritant substances; or sensitisation, in the presence of an allergenic ingredient.

Clinical studies to evaluate the irritation and sensitisation potential of a product must take into account a number of variables: components used in the formulation, ingredient concentration, absorption, amount applied, skin condition, application directions and frequency, as well as the cumulative effect (Dooms-Goossens, 1993).

The objective of such compatibility studies, performed by applying materials to the skin under a patch, is to evaluate potential untoward effects during exaggerated application to the skin to provide assurance that the product is well tolerated and safe for use. A common method to assess the potential of topically applied product to cause irritation or sensitisation involved repeated patch applications of a product to the skin (Basketter, 2008).

The objective of this clinical study is to assess the irritation and sensitisation potential of a cosmetic test product after repeated semi-occlusive patch applications to healthy human subjects by following a conventional HRIPT methodology under supervision of a dermatologist.

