9.2.3. Criteria for Evaluation

The primary evaluation will be to assess the cutaneous irritation and sensitisation potential of the test and control product, based on the irritation (dermal response) and superficial irritation (other effects) score/grade after patch removal during the induction and challenge phase using the ITT population.

Safety and tolerability will be evaluated by adverse events assessments using the Safety population.

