1.2 Study objectives

Objectives	Endpoints
Primary Objective	Primary Endpoint

 To determine the irritation and contact sensitisation potential of a cosmetic facial skin product after repeated patch applications to the skin of healthy subjects. 	
 Trained assessor assessment of local tolerance through visual assessment of cutaneous irritation via the combined dermal response and other effects scores over the induction and challenge phase.
Secondary Objectives	Secondary Endpoint

 To evaluate the general safety of a cosmetic facial skin product. 	
 Assessment of frequency and severity of Adverse Events (AEs)

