1.3 Treatments

	Test Product	Reference Product
Product Name	Facial micellar cleanser	Saline Solution: Sodium chloride (NaCl; 0.9%)
Product Formulation Code (MFC)	CCI	N/A Site to supply
Product Format	200 ml clear PET Bottle	N/A
Application Quantity	0.02 millilitres/square centimetre (ml/cm ²)	0.02 ml/cm ²
Route of Administration	Topical dermal application via semi occlusive patch	
Application Instruction	Applied on-site by technician	

During the Induction Phase there will be a total of 9 patch applications, over 3 consecutive weeks, with patches applied on alternate weekdays each week (Monday, Wednesday, and Friday). Each patch will contain the test product and saline solution. Each patch will remain in place for 48 (± 2) hours on weekdays and 72 hours on weekends. The patch will be removed and the area will be cleaned with saline solution. After 30 minutes (maximum of 1 hour) the site will be graded/evaluated as per the scale in Appendix 2. A new patch of both test product and saline solution will then be reapplied to the same site.

There will then be a two week rest period where no patch applications or assessments are made.

During the Challenge Phase, a naïve site (previously un-patched area) will be selected for the Challenge patch, this area will be graded/evaluated prior to any patch application. A patch with the test product and saline solution will then be randomly applied to the selected previously untreated areas of skin according to the subject's random assignment as determined on Day 1 of the Induction phase. After 48 (± 2) hours, each subject will return for Challenge patch removal, the site will be cleaned with saline solution and graded/evaluated after 30 minutes (maximum of 1 hour). Subjects will return after 24 (± 2) hours and 48 (± 2) hours post patch removal for further grading/assessment.

Document Name	gsk-207585-reporting-and-analysis-plan		
Type	Version	Document Identifier	Effective Date
eldo_controlled	0.1; CURRENT; Most-Recent; Reviewed	090032d580e125d0	
Reason For Issue			

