2.4 Analysis of Dermal Responses

2.4.1 Primary endpoint

2.4.1.1 Primary endpoint definition

The primary analysis will be conducted to assess the cutaneous irritation and sensitisation potential of the test and control product, based on the combined irritation (dermal response) and superficial irritation (other effects) score/grade after patch removal during the induction and challenge phases using the ITT population.

Calculation of combined score (dermal response and superficial irritation):

Document Name	gsk-207585-reporting-and-analysis-plan		
Type	Version	Document Identifier	Effective Date
eldo_controlled	0.1; CURRENT; Most-Recent; Reviewed	090032d580e125d0	
Reason For Issue			

GSK Consumer Healthcare

Confidential

Page 10

Statistical Analysis Plan

207585

The combined score for dermal response and superficial irritation (other effects) will be calculated in the following way –

Combined score = dermal response score + numerical equivalent of the superficial irritation score

Where, the dermal response scale is described in the Table 2 below, and the superficial irritation scores in Table 3 below.

Table 2: Skin Irritation Scoring System (Dermal Response)

CII

Table 3: Superficial Irritation Score System (Symbols and numerical Equivalents)

CII

* The letter grades assigned to the irritation responses will be converted to scores for the statistical analysis process. Grading will be conducted throughout the trial by a qualified staff member.

For example, if the dermal responses score=3 and superficial irritation letter ="C" then the combined score will be:

Combined score = 3 + 2 = 5

 GlaxoSmithKline	Document Name	gsk-207585-reporting-and-analysis-plan		
	Type	Version	Document Identifier	Effective Date
	eldo_controlled	0.1; CURRENT; Most-Recent; Reviewed	090032d580e125d0	
	Reason For Issue			

GSK Consumer Healthcare

Confidential

Page 11

Statistical Analysis Plan

207585

Only subjects with at least one combined score > 0 at any visit will be summarised. The frequency of scores will be summarized in each category of combined score by treatment group and at each time point for both induction and challenge phases. The maximum combined score irrespective of visits for each phase will also be presented ([Table 14.2.1.1](#)). No formal statistical inference will be performed.

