Protocol: 207585

Program Run Date:ddmonyyyy

Table 14.2.1.1
Frequency of Combined Score by Phase, Visit and Treatment and Maximum Combined Score
Intent to Treat Population

Intent to Treat Population (N=XX)

Phase: Induction Phase

Visit	Combined Scores	Facial micellar cleanser		Saline Solution	
		(N=XX)	n	(N=XX)	n
Subjects with at least one combined score > 0 at any visit n (%)		xx (xx.x)		xx (xx.x)	
Subjects with no combined score > 0 at any visit n (%)		xx (xx.x)		xx (xx.x)	
VISIT 2	0	xx		xx	
	1	xx		xx	
	2	xx		xx	
	3	xx		xx	
	4	xx		xx	
	5	xx		xx	
	6	xx		xx	
	7	xx		xx	
VISIT 3		xx		xx	
		xx		xx	
		xx		xx	
VISIT 10		xx		xx	
		xx		xx	
MAXIMUM COMBINED SCORE	1	xx		xx	
	2	xx		xx	
	3	xx		xx	
	4	xx		xx	
	5	xx		xx	
	6	xx		xx	
	7	xx		xx	

Combined Score: Dermal response Score + Superficial response score (>0)

Page x of y

PPD

Programming Note:

- Induction Phase include visit 2 till visit 10.
- Rest Phase include Visit 11
- Challenge Phase include visit 12 till visit 15
- This table is only required if at least one subject reports a combined score >0
- Maximum combined Score will be calculated and displayed at the end of each phase irrespective of visits.

Document Name	gsk-207585-reporting-and-analysis-plan		
Type	Version	Document Identifier	Effective Date
eldo_controlled	0.1; CURRENT; Most-Recent; Reviewed	090032d580e125d0	
Reason For Issue			

Protocol: 207585

Program Run Date:ddmonyyyy

Table 14.2.2.1
Frequency of Dermal Response Score by Phase, Visit and Treatment and Maximum Dermal Response Score
Intent to Treat Population

Intent to Treat Population (N=XX)

Phase: Induction Phase

Visit	Score	Facial micellar cleanser	Saline Solution
		(N=XX)	(N=XX)
		n	n
Subjects with at least one dermal response score > 0 at any visit n (%)		xx (xx.x)	xx (xx.x)
Subjects with no dermal response score > 0 at any visit n (%)		xx (xx.x)	xx (xx.x)
VISIT 2			
0		xx	xx
1		xx	xx
2		xx	xx
3		xx	xx
4		xx	xx
5		xx	xx
6		xx	xx
7		xx	xx
VISIT 3			
VISIT 4			
.....			
VISIT 10			
MAXIMUM DERMAL RESPONSE SCORE		xx	xx
.....			

0 = No evidence of irritation; 1= Minimal erythema barely perceptible; 2 = Definite erythema; readily visible;or minimal edema; minimal popular response; 3 = Erythema and papules;4 = Definite edema; 5 = Erythema, edema and papules; 6 = Vesicular eruption; 7 = Strong reaction spreading beyond test site

Page x of y

Programming Note:

- Induction Phase include visit 2 till visit 10.
- Rest Phase include visit 11
- Repeat for the challenge phase.

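### Once several subjects react, the SAP's tables cannot in general show whether a challenge reaction is new in that subject or exceeds the subject's own saline site

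*SAP*

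**What the plan says.** The objective in SAP 1.2, matched in protocol section 2, opens: "To determine the irritation and contact sensitisation potential of a cosmetic facial skin product". Protocol 9.2.3 likewise sets out to "assess the cutaneous irritation and sensitisation potential of the test and control product". The protocol's introduction treats these as two different processes: "Contact dermatitis can arise from two mechanisms: primary irritation, through the action of irritant substances; or sensitisation, in the presence of an allergenic ingredient".

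For the analysis, SAP 2.4.1.1 states: "The frequency of scores will be summarized in each category of combined score by treatment group and at each time point". It then adds: "The maximum combined score irrespective of visits for each phase will also be presented". Tables 14.2.1.1 (combined score), 14.2.2.1 (dermal response) and 14.2.2.2 (superficial irritation) share one layout. Each has a column per product, a row for subjects with any score above 0, category counts per visit, and the phase maximum. SAP 2.4.1.2 (method) and 2.4.1.3 (supportive analyses) are marked not applicable. The listings in SAP 4.3 cover deaths, adverse events, randomisation and protocol violations. None contains scores.

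The template notes fix the phases: "Rest Phase include Visit 11" and "Challenge Phase include visit 12 till visit 15". For the challenge, SAP 1.3 says that "a naïve site (previously un-patched area) will be selected for the Challenge patch".

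The protocol plans more than the SAP carries over. Sections 3.4 and 6.2.2 and Appendix 2 promise each subject's response per product and reading. Sections 3.4 and 9.3.2 and Appendix 2 promise a written account of every non-zero response. SAP section 3 nevertheless says that the planned analysis is unchanged.

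**The concern.** Sensitisation shows itself within a person: the subject reacts at challenge in a way not seen earlier, and more than at the control site. Neither document says what would count as a sensitisation response, and the SAP's tables show only separate totals for each visit and product. Such totals do not say whether the five people who reacted at challenge are the same five who reacted in induction, or the same five who reacted to saline.

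The phase mapping adds to this. Visit 11 is the reading after the ninth induction patch, and the protocol's schedule (note e) calls it the final induction grading. The SAP tables place it under Rest, although SAP 1.3 says that no assessments occur in the rest period. The Visit 12 reading is taken before the challenge patch goes on, yet it enters the challenge maximum.

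At stake is whether the trial can state how many subjects reacted newly at challenge, which is the quantity behind any statement on sensitisation.

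**Working it through.** **Inputs.** 200 evaluable of 240 randomised, with a bound of 1.8% for zero reactions (SAP 2.8). Table layout and phase mapping from SAP 5.1. The documents give no expected reaction rate, so all reactor counts and scores below are assumptions.

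**1. The plan's own figure.** Exact two-sided 95% upper limit for 0/200: 1 − 0.025^(1/200) = 1.83%, which agrees with the stated 1.8%. The one-sided version, 1 − 0.05^(1/200), is 1.49%. Implied attrition: (240 − 200)/240 = 16.7%. The figure reproduces.

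**2. Challenge against induction.** Two data sets of 200 subjects, all scores 0 except:
- Set A: five subjects score 2 at Visits 8, 9 and 10; five *other* subjects score 2 at Visits 13, 14 and 15.
- Set B: the *same* five subjects score 2 at all six of those visits.

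Each of those visits shows 195 subjects at 0 and 5 at 2 in both sets. Any-response is 5 in induction and 5 in challenge in both. The phase maxima agree. Every cell is the same, yet Set A has five new reactors at challenge and Set B has none.

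In general, with i induction reactors and c challenge reactors among N, the number new at challenge lies between max(0, c − i) and min(c, N − i):

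| i | c | range of new reactors (N = 200) |
|---|---|---|
| 5 | 5 | 0 to 5 |
| 20 | 5 | 0 to 5 |
| 0 | 5 | 5 to 5 |

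For i = c = 5 the rate runs from 0% to 5/200 = 2.5%. The exact upper limit runs from 1.83% (0/200) to 5.74% (the p at which P(X ≤ 5) = 0.025 with n = 200).

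**3. Time course at challenge.** Two reactors with scores (1, 3, 3) and (3, 3, 1) at Visits 13, 14 and 15 give the same table as two with (1, 3, 1) and (3, 3, 3). Visit 13 holds one 1 and one 3, Visit 14 two 3s, Visit 15 one 1 and one 3, and both maxima are 3.

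**4. Test against saline.** Five test-site and five saline-site reactors, all scoring 2, give the same two columns whether they are the same five people (none reacts more to test) or different people (five do).

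**5. Phase mapping.** A score of 3 at Visit 11 only leaves the induction maximum at 0. A score of 1 at Visit 12 only counts as a challenge response.

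**Assumption on the template.** The any-response row, and the SAP's restriction to subjects with a score above 0, are read within the phase and product column in which they appear. If they were applied across the whole study or both sites, the total number of reactors would show (10 against 5 in steps 2 and 4), and those two examples could be separated by subtraction. The pair in step 3 could not.

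**The case against.** A reader might infer that the tables never separate an acquired reaction from plain irritation. They sometimes do:
- A single subject rising 1, 2, 3 differs from one fading 3, 2, 1 at Visits 13 and 15. Only the phase maximum is the same.
- Three challenge-only reactors differ from three induction-only reactors in the any-response, per-visit and maximum rows.
- If nobody reacts in induction, every challenge reactor is new.
- A product that irritates on first contact fills the Visit 3 row; one that reacts only after induction leaves it empty.

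A reader might also infer that nothing planned bears on sensitisation, or that the judgement must rest on narratives read after unblinding. The protocol does plan individual responses and narratives, and a dermatologist is available for same-day secondary grading of a positive reaction (6.2.2). Grading is blinded, and no passage dates the narratives.

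Nor is the 1.8% statement left without a numerator. It is conditional on zero reactions, and the challenge any-response row answers that case, although the documents do not say which kind of reaction is meant.

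Finally, the Rest label for Visit 11 is not peculiar to the SAP: protocol 3.4 also places that reading in the Rest Phase.

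All of this stands and limits the point. It does not remove it. The protocol's subject-level outputs are absent from the SAP's output list, and even if restored they come with no stated criterion for a sensitisation response.

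**Conclusion.** The point holds in a limited form. From the SAP's outputs alone, the sensitisation half of the primary objective cannot in general be answered once several subjects react. With no challenge reactions, the planned tables are enough. In the assumed case of 5/200 reactors per phase, new challenge reactors could be 0 to 5 (0% to 2.5%), with upper limits from 1.83% to 5.74%.

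Separately, the SAP omits the score listing and narratives that the protocol promises, as well as the descriptive statistics on total scores in protocol 9.3.2, while declaring no change.

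The size rests on assumed reactor counts and on reading the any-response row within phase and product. The gap itself does not depend on those counts: no output pairs readings within a subject.

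**What to change.** Before unblinding, from data already collected:

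1. **Listing and narrative.** List dermal, superficial and combined scores at Visits 2 to 15, for both sites, for every subject with any score above 0. Restore the protocol's narrative.
2. **Within-subject table.** Cross-classify post-patch challenge response (Visits 13 to 15, leaving out the pre-patch Visit 12) against post-patch induction response (Visits 3 to 11, keeping Visit 11), by product, with test and saline paired within subject. Show Visit 3 against Visit 13 as the matched first-contact comparison: both are read 30 minutes to 1 hour after a 48-hour patch on previously unpatched skin.
3. **Count.** Report the number of subjects whose challenge response at the test site exceeds their saline site and who had no comparable induction response, with an exact 95% upper limit. Define comparable in the SAP. The denominator should be all ITT subjects with at least one post-patch challenge reading. Requiring every challenge reading could drop a subject who reacts at Visit 13 and then misses Visit 15. Count separately, with their induction scores, those whose challenge was withheld or who dropped out, because protocol 3.4 and 5.2 let the investigator withhold challenge from reactive subjects.
4. **Record** the additions in SAP section 3.

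The cost is one table and one listing. The main limitation is that Visits 14 and 15 have no matched induction reading, since the site is re-patched after Visit 3. Some late irritant responses may therefore be counted. The count should be read as a descriptive screen beside the listing and narratives.

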2.4.1.2 Statistical hypothesis, model, and method of analysis

Not Applicable.

2.4.1.3 Supportive analyses

Not Applicable.

2.4.2 Handling of missing values/censoring/discontinuations

Missing data will not be replaced or imputed. Dropouts will be included in analyses up to the point of discontinuation.

2.5 Analysis of secondary objectives

2.5.1 Dermal Response (secondary)

Not Applicable.

2.5.2 Safety

2.5.2.1 Adverse events and Serious Adverse Events

All adverse events (AEs) will be summarised by primary system organ class and preferred term.

Treatment emergent adverse events (TEAEs) will be summarized by the number and percentage of subjects having any adverse event, an adverse event in each System Organ Class, and each individual adverse event ([Table 14.3.1.1](#)). All TEAEs will also be tabulated by severity ([Table 14.3.1.2](#)). Treatment-emergent AEs suspected of a relationship to study medication and those causing study discontinuation will be presented in a similar manner ([Table 14.3.1.3](#)). For treatment-related AEs, these will also be presented by severity, if applicable ([Table 14.3.1.4](#)).

Additionally, all treatment-emergent adverse events will be listed.

Deaths occurring during treatment (if any) will be listed ([Listing 14.3.2.1](#)) by treatment, including the date and study day of death, and the principal cause of death. Non-fatal serious

Document Name	gsk-207585-reporting-and-analysis-plan		
Type	Version	Document Identifier	Effective Date
eldo_controlled	0.1; CURRENT; Most-Recent; Reviewed	090032d580e125d0	
Reason For Issue			

GSK Consumer Healthcare

Confidential

Page 12

Statistical Analysis Plan

207585

adverse events and adverse events causing study treatment discontinuation will be listed ([Listing 14.3.2.2](#)).

All AEs will be listed in the [Listing 16.2.7.1](#) and [Listing 16.2.7.2](#)

2.6 Analysis of other variables

Not applicable.

2.7 Interim analysis

No interim analysis is planned.

2.8 Sample size calculation

Approximately 280 healthy subjects were screened to randomize at least 240 subjects to ensure 200 evaluable subjects complete the entire study. If no reaction is observed in 200 subjects, there is a 95% certainty that the actual rate of reactions in the wider population is <1.8%.

3 Changes to the Protocol Defined Statistical Analysis Plan

There were no changes or deviations to the originally planned statistical analysis specified in the [protocol version 1.0 \[\(Dated: 31/JAN/2017\)\]](#).

 GlaxoSmithKline	Document Name	gsk-207585-reporting-and-analysis-plan		
	Type	Version	Document Identifier	Effective Date
	eldo_controlled	0.1; CURRENT; Most-Recent; Reviewed	090032d580e125d0	
	Reason For Issue			

4 Appendix 1:

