Type and Planned Number of Subjects

Approximately 280 healthy subjects will be screened to randomize at least 240 subjects to ensure 200 evaluable subjects complete the entire study. If no reaction is observed in 200 subjects, there is a 95% certainty that the actual rate of reaction in the wider population is <1.8%.

Diagnosis and Main Criteria for Inclusion

Healthy male and female volunteers aged 18 to 65 with no dermatological disorders, with a Fitzpatrick skin phototype I to IV will be enrolled into this study.

Product Information

| | Test Product | Reference Product | |
|--------------------------|---|--|--|
| Product Name | Facial micellar cleanser | Saline Solution: Sodium Chloride (NaCl; 0.9%) | |
| Product Formulation | CCI | N/A | |
| Code (MFC) | | Site to supply | |
| Product Format | 200ml clear PET Bottle N/A | | |
| Application Quantity | 0.02 millilitres/square | 0.02 ml/cm^2 | |
| | centimetre (ml/cm ²) | | |
| Route of Administration | Topical dermal application via semi occlusive patch | | |
| Application Instructions | Applied on-site by technician | | |

Statistical Methods

The focus of the statistical analysis will be the evaluation of the frequency and level of irritation and sensitisation responses of the investigational product. All subjects with any product applied will be included in the analysis population.

Individual observations will be assessed based on Appendix 2 and a narrative description of all skin responses, both in the induction and challenge phases, will be provided. A frequency tabulation of the number of subjects with any skin response versus those without any skin response will be presented by treatment group for both the induction and challenge phases of the study. If there are subjects with non-zero dermal response or superficial irritation scores, a combined dermal and others effects

| Document Name |   | | |
|----------------------|---|---------------------|----------------------|
| Туре | Version | Document Identifier | Effective Date |
| eldo climitralleatoc | 0.0; CURRENT; Most-Recent; Rfferietiwed | 090032d580e42566 | 31-Jan-2017 14:20:06 |
| Reason For Issue | Auto Issue | | |

score will be determined across all time points over the induction and challenges phases as well as at each assessment time point and summarised using descriptive statistics.

No interim or subgroup analyses are planned.

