After the last patch removal and grading/evaluation of the Induction Phase, subjects will enter a Rest Phase of 2 weeks. During this time there will be no product patch applications.

| Document Name | @sikvi20179@sitqurot@07 1585 | | |
|-----------------------|---------------------------------------|---------------------|----------------------|
| Туре | Version | Document Identifier | Effective Date |
| eldo climitarelleatoc | 0.0; CURRENT; Most-Recent; Revietived | 090032d580e42d66 | 31-Jan-2017 14:20:06 |
| Reason For Issue | Auto Issue | | |

Challenge Phase:

After completing the Rest Phase, subjects will return for the Challenge Phase. A naïve site (previously un-patched area) will be selected for the Challenge patch, this area will be graded/evaluated prior to any patch application. A patch with the test product and saline solution will then be randomly applied to the selected previously untreated areas of skin according to the subject's random assignment as determined on Day 1 of the Induction phase. After $48 (\pm 2)$ hours, each subject will return for Challenge patch removal, the site will be cleaned with saline solution and graded/evaluated after 30 minutes (maximum of 1 hour). Subjects will return after 24 (± 2) hours and $48 (\pm 2)$ hours post patch removal for further grading/assessment.

End of Study:

After the 48-(\pm 2) hour grading/assessment, a final clinical assessment by a qualified dermatologist will be performed to confirm it is medically appropriate to exit the subject from the study. After all study assessments are completed, subjects will be discharged from the study site.

Adverse events and concomitant medications will be assessed throughout the study.

Patch Assessments:

The results of the patch site assessments (Appendix 2) will be presented as individual responses to each test product and the negative control (saline solution) at each assessment time point. All responses will be reviewed in context of the grading scale.

Assessment of the patch sites will be conducted once at Baseline (Visit 2/Day 1) prior to any patch applications and then a further 8 times post-baseline during the Induction Phase, once during the Rest Phase (for the final Induction Phase patch removal), and four times during the Challenge Phase (prior to Challenge patch application and post) by a blinded assessor (a qualified staff member).

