9.3.2. Primary Analysis(es)

The primary analysis will be based on the irritation (dermal response) and superficial irritation (other effects) scores/grades assessed using the scales described in Tables 1 and 2 of Appendix 2. Individual observations will be assessed based on these scales and a narrative description of all skin responses, both in the induction and challenge phases, will be provided.

No formal statistical inference will be performed.

The number and percentage of subjects recording each category of score/grade, as well as any skin response versus those without any skin response will be presented by treatment group at each assessment time point and over the induction and challenge phases using the maximum grade/score. If there are subjects with non-zero dermal response or other effects scores, then the dermal response, other effects and a combined dermal and others effects score will be summarised using descriptive statistics at each assessment time point and over the induction and challenges phases using a total score across time points.

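### SAP section 3 declares no changes, but the SAP leaves out the descriptive and total-score summaries of the skin scores that protocol 9.3.2 plans

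*SAP*

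**What the plan says.** **Protocol.** Section 9.3.2 (Primary Analysis) has three parts.

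- Category tables: "The number and percentage of subjects recording each category of score/grade", with any response against none, by product, at each time point and by phase using the maximum.
- If any score is non-zero, the dermal, other-effects and combined scores are to be "summarised using descriptive statistics at each assessment time point and over the induction and challenges phases using a total score across time points".
- Narratives: "a narrative description of all skin responses, both in the induction and challenge phases, will be provided".

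The synopsis repeats the second part for the combined score alone: that "score will be determined across all time points over the induction and challenges phases as well as at each assessment time point", with descriptive statistics. Section 3.4 adds: "The results of the patch site assessments (Appendix 2) will be presented as individual responses to each test product" and to saline, at each time point. Section 6.2.2 and Appendix 2 say much the same.

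**SAP.** For the combined score, section 2.4.1.1 says "The frequency of scores will be summarized in each category of combined score by treatment group and at each time point", and then "The maximum combined score irrespective of visits for each phase will also be presented". The dermal and superficial scores are treated the same way. Supportive analyses (2.4.1.3) are marked not applicable. The skin outputs in list 4.2 are Tables 14.2.1.1, 14.2.2.1 and 14.2.2.2. The six listings in 4.3 cover deaths, serious adverse events leading to discontinuation, randomisation, protocol violations, and adverse events (two listings). Section 3 then states: "There were no changes or deviations to the originally planned statistical analysis specified in the" version 1.0 protocol.

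**The concern.** The SAP's introduction says that it describes the analyses and outputs for the study report, so anything missing from it is likely to be missing from the report. Part of what is missing stands under the protocol's own primary-analysis heading, and section 3 tells the reader that nothing was altered.

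At stake is how fully the report describes reactions if there are any. The design applies the product nine times to see whether irritation accumulates or sensitisation develops. The total score is the one planned summary that shows how much reaction each subject accumulated. A phase maximum does not show it: one weak reading and nine weak readings both have a maximum of 1.

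**Working it through.** The plan gives no figure on this point, and neither document plans formal inference. The check is therefore a comparison of texts, followed by a small example of what the planned tables can and cannot show.

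**1. Protocol outputs against the SAP**

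| Protocol output | In the SAP? |
|---|---|
| Category counts per visit | Yes |
| Category percentages per visit | No; the shells show n only |
| Any response against none | Yes, with percentages |
| Phase maximum | Yes |
| Descriptive statistics per time point (three scores) | No |
| Total score across time points (three scores) | No; not defined anywhere |
| Individual responses by product and time point | No; 0 of 6 listings |
| Narratives of skin responses | Not mentioned |

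The scale tables in SAP 2.4.1.1 are redacted, but the output lists and shells are visible, so redaction does not explain the gaps.

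**2. What the counts still give**

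If n_k subjects score k at a visit and n were read, the visit mean is Σ k·n_k / n. With complete data, the mean total is the sum of the visit means. Neither mean is lost, provided every score that occurs has its own row.

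**3. What they do not give**

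Take two reactors, A and B, at one product site. The induction readings are at Visits 3 to 11 (nine). Each reaction is a dermal score of 1 with nothing added for superficial irritation, so the combined score is 1. No score reaches 3, so no patch is moved. These scores are illustrative; the documents give no expected pattern.

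- Case 1: A scores 1 at all nine visits and B at Visit 3 only. The totals are 9 and 1.
- Case 2: A scores 1 at Visits 3–7 and B at Visits 3 and 8–11. The totals are 5 and 5.

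In both cases the counts of score 1 by visit are 2, 1, 1, 1, 1, 1, 1, 1, 1, and both subjects have a maximum of 1. The tables are identical.

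- Mean total, both cases: (2 + 8 × 1) / 2 = 5.
- SD, case 1: √[((9 − 5)² + (1 − 5)²) / 1] = √32 = 5.66.
- SD, case 2: 0.

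If Visit 11 is left out, as in the shells, eight readings remain. Case 1 becomes 8 and 1, and case 2 becomes 5 and 4. The mean is (2 + 7 × 1) / 2 = 4.5 in both. The SDs are √(3.5² + 3.5²) = 4.95 and √(0.5² + 0.5²) = 0.71. The tables again do not distinguish the two cases.

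**4. Visit 11**

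- Treated as the last induction reading: protocol Schedule of Events (note e), protocol 6.2.2 and SAP 1.1. SAP 1.3 adds that nothing is assessed during rest.
- Placed in rest: protocol 3.4, the programming notes to the three skin-table shells, and a footnote to Listing 16.2.2.

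As programmed, the induction maximum covers Visits 2 to 10. It takes in the baseline reading, made before any patch, and leaves out the reading after the ninth application. The challenge block likewise takes in the pre-patch reading at Visit 12. Yet protocol 9.2.3 and SAP 2.4.1.1 base the primary evaluation on scores after patch removal.

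**The case against.** The strongest reply is that little is lost.

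- **Persistent against single reactions.** A reader might infer that the SAP cannot separate a reaction at every reading from a single one. That goes too far. The maximum cannot, but the per-visit counts can when there is one reactor: a persistent reaction appears in every visit row and a single one in one row. The loss is confined to how totals are spread among several reactors.
- **Narratives.** A reader might infer that the narratives have been dropped, or that the link between a subject's test and saline sites cannot be recovered. The documents support neither. The SAP is silent, the narratives may be written directly in the report, and narratives of every score above 0 could supply that link.
- **Listing.** The call for individual responses is in protocol 3.4, 6.2.2 and Appendix 2, not in the table plan of 9.3.2, and one phrase in Appendix 2 may describe data recording. The missing listing is a real output gap, because 3.4 and 6.2.2 speak of presenting the responses. It is weaker evidence that section 3 is wrong.
- **Visit 11.** The shells follow protocol 3.4, so this is not an undeclared change. It is an inconsistency within the protocol, which the SAP repeats.
- **Synopsis.** It covers only the combined score and does not use the word total. The commitment rests on 9.3.2.
- **Percentages.** Their absence is minor, since N and every category count are shown.

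These replies narrow the point. None of them supplies the summaries planned in 9.3.2 or makes the section 3 statement correct.

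**Conclusion.** The point holds in a limited form. The SAP omits the descriptive statistics and the total score that protocol 9.3.2 plans for three skin scores, and section 3 wrongly reports no change. The information lost is the distribution of subject totals when more than one subject reacts: in the example, an SD of 5.66 or 0 behind the same tables (4.95 or 0.71 without Visit 11).

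Two related gaps stand beside it. No listing shows individual skin scores, and the induction maximum omits the reading after the ninth application.

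The conclusion assumes that at least one score is non-zero, because the protocol makes these summaries conditional on that. If no subject reacts, their omission costs nothing. Recovery of the means also assumes complete data. A reader might infer that the study's conclusions or its sample-size statement are undermined; nothing here touches either. This should be corrected, but it does not invalidate the design.

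**What to change.** 1. Restore the descriptive and total-score summaries for the dermal, other-effects and combined scores, or record their removal with a reason. Correct the statement in section 3 either way. If restored, say whether there is one total per phase or one across both. Show the number of readings behind each total: patching can stop after a repeat combined score of 3 or more, and missing data are not imputed, so totals may rest on different numbers of readings.
2. Add to SAP 4.3 a by-subject listing of dermal, superficial and combined scores by product, skin site graded (original, adjacent or challenge) and visit. State where the narratives will be given.
3. Reconcile the phase of Visit 11 across both documents so that the reading after the ninth application enters the induction summaries and maximum. Keep the pre-patch readings at Visits 2 and 12 out of the post-removal maxima and totals. Category percentages can be added to the shells at the same time.

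The cost is slightly more output, all from data already collected, with no effect on subjects. The SAP text is marked version 0.1 and is to be finalised before database freeze and unblinding; the change belongs before that point.
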